A different pattern is seen in the criterion data, plotted in Figure 5. Here, there are two clear clusters of significant effects. When block 1 has low prevalence and feedback, criterion on block 2 is more conservative (Pairs where Block 1 is low prevalence with feedback, all $p < 0.006$, Cohen's d between 0.2 and 0.5). When block 1 has high prevalence and feedback, criterion on block 2 is more liberal (Pairs where Block 1 is high prevalence with feedback, $p < 0.0005$, pair

44, $p = 0.017$; note that there are only 27 pairs of this variety in the dataset, All Cohen's d between 0.2 and 0.5). When block 1 does not have feedback, there is no effect on criterion in pair 2, except, perhaps, for 'high feedback' on Block 2 ($p < 0.028$, again, not corrected for multiple comparisons, Cohen's $d = 0.18$). This is the main finding of the paper. Criterion can be manipulated by the prevalence of the preceding block of trials, but only if the participants received feedback on that first block.

[figure not shown]

Figure 5: Change in criterion on block 2 as a function of the nature of block 1. P-values
show results for simple t-tests, testing against the null hypothesis that there is no change in
criterion. Black lines show means +/- 95% confidence intervals.

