first half and second half of the trials in block 2, separately. The results are essentially unchanged from those shown in Figure 5. Exposure to Low Prevalence with Feedback in block 1, produces a conservative shift in block 2 criterion in both the first half and the second half of block 2. All t-tests for pairs where Block 1 is Low Feedback are significant except for the Low Feedback → High Feedback pair in the first half, when the effect should be stronger than in the second half. Exposure to High Prevalence with Feedback in block 1, produces a liberal shift in block 2 criterion in both the first half and the second half of block 2. T-tests when block 2 is Low Feedback, Low No Feedback and High No Feedback are significant. T-test when block 2 is High Feedback is not significant in either half (again, recall that the High Feedback -> High Feedback pair has the fewest instances in the dataset).

The lack of any systematic decrease in the magnitude of the effects is shown in Figure 8. The mean change in criterion is plotted for the first and second half of each pair of blocks. Note the grouping of the pairs. The dark blue pairs show the conservative (positive) shift following low prevalence with feedback. The red pairs show the liberal (negative) shift following high prevalence with feedback. If the effects only lasted for the first 2-3 dozen trials, these effects should collapse toward zero in the second half. Clearly, this is not the case.

[figure not shown]

Figure 8: Mean change in criterion for the first and second halves of a block of trials.

Effects of Expertise

As noted in the Methods section, participants gave a rough categorization of their level of expertise. Sadly, this convenience population does not include any substantial number of self-identified expert dermatologists. Only one MD self-identifies as a dermatologist. We can create an expertise continuum from participants reporting no medical training to premedical students to medical students and, finally, to medical doctors. Table 6 shows the numbers of participants and the number of pairs of data contributed by each group.

Expertise category	No. of Participants	No. of pairs
Medical Doctor	54	131
Medical Student	337	952
Pre-Med Student	174	426
No Medical Experience	145	358

Table 6: Number of participants in each expertise group and the number of condition pairs contributed by the groups.

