Figure 9 shows d' and criterion as a function of expertise group, regardless of the type of feedback or prevalence (Recall, from Figure 2, that there is little effect of block type on d' .)

[figure not shown]

Figure 9: Effects of expertise category on d' and crit, regardless of prevalence and/or feedback.

There is a highly significant effect of expertise category ($F(3, 1863) = 38.58, p < 0.0001$, partial eta-squared = 0.86) and, as can be seen by the pairwise comparisons, that effect is entirely due to superior performance of the medical students (all comparisons to medical students, $p \leq 0.0001$).

It might seem disappointing that MDs were no better at this task than non-medical participants.

However, these non-dermatologist MDs may not have spent time looking at skin lesions for many years and the novices were only being asked to perform a difficult, but straight-forward, two-alternative, forced-choice discrimination. It is the medical students, many of whom may have recently been learning about skin lesions, who do somewhat better on this task. Of course, there could be other reasons for the group differences (e.g. motivated, competitive students versus more casually interested MDs. We cannot know in this case.)

There is a very modest effect of expertise category on criterion ($F(3, 1863) = 3.32, p = 0.02$, partial eta-squared = 0.01). Pairwise comparisons reveal that premedical students are slightly more conservative than medical students ($p = 0.049$). This does not appear to be a particularly meaningful finding.

In terms of the impact of expertise on the effect of block 1 on block 2, the data are noisy, with fewer pairs showing significant effects of block 1 on block 2. This seems to be a statistical power issue. The pairs that are significant are the same as those seen in Figure 4, with low prevalence on block 1 making participants more conservative on block 2 and high prevalence making them more liberal. There is no evidence for any systematic effect of expertise. In particular, there is no evidence that the most expert group (medical students) shows a different pattern of results. In

that group (fortunately, the largest), Pairs with Low Feedback as block 1 are more conservative and with High Feedback as block 1 are more liberal (all $p \leq 0.01$).

Literature Cited

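### The medical-student bound of p ≤ 0.01 for every feedback-first pair is doubtful for the High-Feedback repeat pair, where all 27 pairs give only p = 0.017, and the two statements need reconciling

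*Combined protocol and SAP*

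**What the plan says.** The relevant text is in the Specific Protocol part of the combined protocol and SAP.

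- **How does one block influence the next?** Change in criterion is tested pair by pair with one-sample t-tests. The High-Feedback-first pairs are at p < 0.0005, except the High-Feedback repeat (pair 44) at p = 0.017, with the caution "note that there are only 27 pairs of this variety in the dataset". For the High-Feedback-first group the effect sizes are given as "All Cohen's d between 0.2 and 0.5". The Low-Feedback-first pairs are all below p = 0.006.
- **Does the effect of one block last throughout the next block?** The High-Feedback repeat is not significant in either half of block 2, and its small count is mentioned again.
- **Effects of Expertise.** The subgroup results are called noisy, with fewer significant pairs, and this is put down to power. The text then says "there is no evidence that the most expert group (medical students) shows a different pattern of results", and for that group: "Pairs with Low Feedback as block 1 are more conservative and with High Feedback as block 1 are more liberal", with p ≤ 0.01 attached to all of them.
- **Tables 5 and 6.** There are 2,080 filtered pairs, of which medical students contribute 952.

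No cell counts, means, SDs or individual p-values are printed for students. No test compares students with the other groups.

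**The concern.** Read pair by pair, the student bound covers eight cells, one of which is the High-Feedback repeat. That cell reaches only p = 0.017 with everyone included, yet a subset of it is said to reach 0.01 or less. Wherever the document reports this cell's criterion shift on its own, it treats it as the weak one. The student sentence drops that exception in a smaller sample, just after saying that subgroup power is low.

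The sentence carries weight because it gives the only group-specific p-values for carry-over by expertise. A reader will take it as a clean replication in the largest and best-performing group, and as the main support for saying that expertise has no systematic effect. Nothing printed lets the reader check it.

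**Working it through.** **Inputs.** Pair 44 in the full data: n = 27, p = 0.017 (How does one block influence the next?; n also in Table 5). Student pairs: 952 (Table 6). All filtered pairs: 2,080 (Table 5). Student bound: p ≤ 0.01 (Effects of Expertise). Sidedness is not stated, so two-sided tests are assumed. Pairs are treated as independent, as in the document's own t-tests.

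**1. Reproduce the stated full-data result.** For a one-sample t-test, d = t/√n. Two-sided p = 0.017 on 26 df gives t = 2.55, so d = 2.55/√27 = 0.49. A one-sided test would give d = 0.43. Both lie in the stated range of 0.2 to 0.5, so the p-value, n and effect size agree. Table 6 also ties out: 131 + 952 + 426 + 358 = 1,867, and 1,867 − 4 = 1,863, the printed error df.

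**2. Student count in this cell.** It is not reported. A proportionate share is 27 × 952/2,080 = 12.4, so 12 is used, with a range around it.

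**3. What the full-data effect would give in students.** With d = 0.49 and n = 12, t = 0.49 × √12 = 1.70 on 11 df, p = 0.12.

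**4. What the bound requires, and how often chance supplies it.** Required d = t(0.995, n − 1)/√n; at n = 12 this is 3.11/√12 = 0.90. The last column simulates random subsets of 27 normal values whose overall p is exactly 0.017.

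| Student pairs | p if d = 0.49 | d needed for p ≤ 0.01 | Chance that a random subset reaches it |
|---|---|---|---|
| 8 | 0.21 | 1.24 | 5% |
| 10 | 0.16 | 1.03 | 6% |
| 12 | 0.12 | 0.90 | 7% |
| 16 | 0.07 | 0.74 | 10% |
| 20 | 0.04 | 0.64 | 13% |
| 24 | 0.02 | 0.57 | 14% |

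Even if all 27 pairs were students', the bound would need d = 0.53, and the observed p would still be 0.017. So at every possible count students must show an observed d above 0.49. If 0.49 is instead taken as the true effect, 12 pairs reach p ≤ 0.01 about 13% of the time.

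**5. Would the bound, if right, show a larger effect in students?** Put 12 students exactly at p = 0.01 and assume a common within-group SD s. In units of the overall SD, the sum of squares 25s² + 12(m₁ − 0.49)² + 15(m₂ − 0.49)² = 26, with m₁ = 0.897s, gives s = 0.96, m₁ = 0.86 and m₂ = (27 × 0.491 − 12 × 0.861)/15 = 0.195, about 0.2. The difference has t = (0.861 − 0.195)/(0.96 × √(1/12 + 1/15)) = 1.79 on 25 df, p of about 0.09. The same calculation gives p = 0.03 at 8 student pairs and 0.15 at 16. Among simulated subsets that reach p ≤ 0.01, about 70% (n = 12) to 80% (n = 20) show no significant student-versus-others difference.

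**The case against.** A reader might infer that one of two things must be true: the bound is misprinted, or carry-over is clearly larger in students and the statement about pattern is false. The documents support neither as a necessity.

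- **Chance.** A subset can have a smaller p than the whole. At 5% to 14% this is unexpected but not remarkable.
- **Spread.** d is a mean over an SD. Twelve students with exactly the overall mean shift reach p = 0.01 if their SD is 0.49/0.90 = 0.55 of the overall SD (0.77 for 20 pairs). A larger mean shift is not required, and no SDs are printed.
- **Pooling.** If the bound refers to two pooled tests, the conflict disappears: about 496 × 952/2,080 = 227 High-Feedback-first student pairs at d = 0.2 give p = 0.003. However, no pooled test is mentioned, and the full-data section uses the same phrasing for individual pairs.
- **Meaning of pattern.** In that section it means which pairs shift and in which direction. A larger shift in the same direction would not contradict it.

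It is also tempting to extend the point to the other seven feedback-first cells. Their full-data p-values are printed only as upper bounds (below 0.006 or below 0.0005), so they neither confirm nor refute the student bound.

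Finally, the document does warn that this cell is small and that the subgroup results are noisy, and the main finding rests on the full data. All of this stands and limits the point to one cell. It does not explain why the exception made for that cell in the full data is missing for students.

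**Conclusion.** The p ≤ 0.01 claim for medical students is doubtful for the High-Feedback repeat pair and has to be reconciled with p = 0.017 in all 27 pairs. At about 12 student pairs the observed d must be about 0.90, or 1.8 times the full-data value; a random subset achieves that about 7% of the time. No error is proven, and no larger student effect is shown. The figures assume two-sided per-pair tests, independent pairs and, for the central case, a proportionate student share.

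The wider weakness does not depend on that share. The absence of an expertise effect is argued from which cells are significant within subgroups, and no direct comparison is reported. The full-data finding on carry-over is not affected.

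**What to change.** 1. Re-run the eight medical-student feedback-first cells from the posted pair data. Print n, mean criterion shift, SD, 95% CI and exact p for each.
2. Correct the bound, or state which cells or pooled tests it covers. If the High-Feedback repeat is an exception in students too, say so, as the full-data section does.
3. Base the conclusion on expertise on the estimated student-minus-others difference in the sign-aligned criterion shift (High-Feedback-first shifts reversed in sign, so that a positive value is the expected direction). Give its 95% CI and allow for repeated pairs per participant, for example with a participant random effect or clustered standard errors. Do not infer similarity from significance within subgroups.

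The cost is one re-run of an existing analysis, one added contrast and one or two revised sentences. No new data are needed, provided the posted file carries the expertise category and participant number or these can be linked to it.
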